Appendix G Classification of Tumour Lysis Syndrome

G 1 Classification

The criteria for classification of laboratory and clinical TLS in adults are described below. These criteria are based on the Howard et al 2011 ([Howard et al 2011](#)) modification of Cairo and Bishop 2004 ([Cairo and Bishop 2004](#)), and have been adapted from Cheson et al 2017 ([Cheson et al 2017](#)).

Clinical TLS assumes the laboratory evidence of metabolic changes and an adverse event that requires clinical intervention. Clinical TLS is defined as the presence of laboratory TLS and any one or more of the clinical criteria, as specified in [Table G31](#) below.

Table G31 Criteria for Laboratory and Clinical Tumour Lysis Syndrome

Abnormality	Criteria
Laboratory TLS	
Two or more of the following metabolic abnormalities occurring during the same 24-hour period, and within 3 days before until 7 days after infusion of study intervention:	
Hyperuricaemia	Uric acid $\geq 475.8 \mu\text{mol/L}$ ($\geq 8.0 \text{ mg/dL}$)
Hyperkalaemia	Potassium $\geq 6.0 \text{ mmol/L}$
Hyperphosphataemia	Phosphate $\geq 1.5 \text{ mmol/L}$ ($\geq 1.5 \text{ mg/dL}$)
Hypocalcaemia	Corrected calcium $< 1.75 \text{ mmol/L}$ ($< 7.0 \text{ mg/dL}$), or Ionised calcium $< 0.3 \text{ mmol/L}$
Clinical TLS	
Laboratory TLS plus one or more of the following:	
Acute kidney injury	Serum creatinine increase by $> 26.5 \mu\text{mol/L}$ (or a single value $> 1.5 \times \text{ULN}$ if no baseline measurement), or oliguria (average urine output of $< 0.5 \text{ mL/kg/h}$) lasting for $> 6 \text{ hours}$
Cardiac arrhythmia/dysrhythmia or sudden death	Probably or definitely caused by hyperkalaemia or hypocalcaemia
Seizure	Probably or definitely caused by hypocalcaemia
Neuromuscular irritability, hypotension, or heart failure	Probably or definitely caused by hypocalcaemia

TLS = tumour lysis syndrome; ULN = upper limit of normal.

G 2 Grading

Tumour lysis syndrome should be graded according to the Cairo-Bishop criteria for the purposes of dose-limiting toxicity assessment ([Cairo and Bishop 2004](#)). The grade of the maximal clinical manifestation defines the overall grade of TLS, as summarised below in [Table G32](#).

Table G32 Grading of Tumour Lysis Syndrome

Cairo-Bishop Grading for TLS						
Abnormality	Grade 0	Grade 1	Grade 2	Grade 3	Grade 4	Grade 5
Laboratory TLS	Absent	Present	Present	Present	Present	Present
Serum creatinine ^a	$\leq 1.5 \times \text{ULN}$	$1.5 \times \text{ULN}$	$1.5 - 3.0 \times \text{ULN}$	$> 3.0 - 6.0 \times \text{ULN}$	$> 6.0 \times \text{ULN}$	Death ^b
Cardiac arrhythmia ^a	None	Intervention not indicated	Nonurgent medical intervention indicated	Symptomatic and incompletely controlled medically, or controlled with device (eg, defibrillator)	Life-threatening (eg, arrhythmia associated with CHF, hypotension, syncope, shock)	Death ^b
Seizure ^a	None	--	One brief generalised seizure; seizures well controlled by anticonvulsants; infrequent focal motor seizures not interfering with ADL	Seizure in which consciousness is altered; poorly controlled seizure disorder; with breakthrough generalised seizures despite medical intervention	Seizure of any kind and prolonged, repetitive, or difficult to control (eg, status epilepticus, intractable epilepsy)	Death ^b

^a Not directly or probably attributable to therapeutic agent.

^b Probably or definitely attributable to clinical TLS.

Modified from Cairo and Bishop 2004.

ADL = activities of daily living; CHF = congestive heart failure; TLS = tumour lysis syndrome; ULN = upper limit of normal.

G 3 References

Cairo and Bishop 2004

Cheson et al 2017

Howard et al 2011

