5 STUDY POPULATION – CORE

Prospective approval of protocol deviations to recruitment and enrolment criteria, also known as protocol waivers or exemptions, is not permitted.

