5.1 Inclusion Criteria

Patients are eligible to be included in the study only if all of the core criteria below and all criteria from the relevant individual modules apply. Where specific module criteria differ from core inclusion criteria, the most stringent criteria should be applied.

Informed Consent

- 1 Provision of signed and dated written informed consent, as described in [Appendix A](#), prior to any study-specific procedures, sampling, and analyses. Informed consent includes compliance with the requirements and restrictions listed in the ICF and in this CSP.

Age

- 2 Patient must be aged \geq 18 years at the time of signing the informed consent. In some countries, parental consent may be required in addition to an assent form for patients who are 18 years of age.

Type of Patient and Disease Characteristics

- 3 Patient must have histologically documented diagnosis of B-NHL as defined by a B-cell neoplasm in the World Health Organisation classification scheme except as noted in the exclusion criteria.
- 4 Patient has relapsed after or failed to respond to at least 2 but no more than 5 prior systemic treatment regimens (including investigational therapy) and for whom there is no available therapy expected to improve survival (eg, standard chemotherapy, autologous SCT, CAR-T cell therapy).
- 5 Documented active disease requiring treatment that is relapsed or refractory defined as:
 - Recurrence/relapse of disease after response to prior line(s) of therapy.
 - Progressive disease (refractory) on/after completion of the treatment regimen preceding entry into the study.
- 6 Must have at least one measurable FDG-PET avid lesion (except for MZL), based on bi-dimensional assessment on PET and CT/MRI scan. A measurable lesion is defined as:
 - For nodal lesions: longest diameter > 1.5 cm
 - For extranodal lesions: longest diameter > 1 cm
- 7 ECOG performance status score ≤ 2 . Performance status must not have deteriorated by ≥ 2 levels within 2 weeks after providing informed consent.
- 8 Adequate haematologic, hepatic, and renal function as defined in [Table 3](#).

Table 3 Criteria for Adequate Organ and Marrow Function

Parameter	Criteria	
Haematologic	Haemoglobin	$\geq 8.0 \text{ g/dL (5.59 mmol/L)}$ with no whole blood transfusions within 14 days prior first dose of AZD0466

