8.2.4 Clinical Safety Laboratory Assessments

Blood and urine samples for determination of clinical chemistry, haematology, coagulation, urinalysis, viral serology, pregnancy, and other laboratory tests will be taken at the visits indicated in the SoA of the relevant individual module. Collection times begin from the start of the infusion.

The date and time of each collection will be recorded in the appropriate eCRF. Following SRC review of emerging data, the timing of laboratory safety assessment samples may be adjusted for subsequent cohorts. Additional sampling times may be added or removed if indicated by the emerging data.

Additional safety samples may be collected if clinically indicated at the discretion of the Investigator. The date, time of collection, and results (values, units, and reference ranges) will be recorded on the appropriate eCRF. Laboratory values will be repeated, confirmed, and followed up as appropriate.

Situations in which laboratory safety results should be reported as AEs are described in Section [8.3.5](#).

All laboratory safety analyses, including clinical chemistry, haematology, and urinalysis, will be performed at a local laboratory at or near to the Investigator site. Sample tubes and sample sizes may vary depending on laboratory method used and routine practice at the site.

Pregnancy tests may be performed at the site using a licensed test (urine or serum pregnancy test). Abnormal clinically significant laboratory results should be repeated as soon as possible (preferably within 24 to 48 hours).

The laboratory safety variables listed in [Table 12](#) will be measured.

Table 12 Laboratory Safety Variables

Haematology/Haemostasis (whole blood)		Clinical Chemistry (serum or plasma)	
Haemoglobin (Hb)		Creatinine	Chloride
Leukocyte count (WBC count)		Bilirubin, total	Cortisol ^a
Leukocyte differential count		Alkaline phosphatase	TSH ^a
Neutrophils		AST	Bicarbonate
Lymphocytes		ALT	BUN/urea nitrogen
Eosinophils		Amylase ^b	Lipase ^b
Platelet count		Albumin	LDH
Urinalysis		Potassium	Phosphate
Hb/erythrocytes/blood		Calcium, total	Uric acid
pH	Ketones	Sodium	Troponin I ^a
Protein/albumin	Bilirubin	BNP (or NTproBNP) ^a	
Glucose		Magnesium	Glucose
Microscopy (red and white blood cells, bacteria, casts, and crystals) only if urinalysis is abnormal		Total protein	ACTH ^a
Coagulation		Cholesterol	GGT
International normalised ratio (INR)		Triglycerides	Ferritin

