	High	Intermediate	Low
Anti-hyperuricemics	Allopurinol 100 to 300 mg every 8 hours Early consideration of rasburicase ^a as an alternative, based on baseline uric acid and tumour burden		Allopurinol 100 to 300 mg every 8 hours
Criteria for use of rasburicase			
Serum uric acid at baseline	> 475.8 µmol/L ^b + 1 risk factor ≤ 475.8 µmol/L ^b + 2 risk factors	> 475.8 µmol/L ^b + 2 risk factors ≤ 475.8 µmol/L ^b + 3 risk factors	NA
Risk factors	Serum creatinine > 1.3 mg/dL (> 88.4 µmol/L) WBC > 50 × 10 ⁹ /L LDH > 2 × ULN		NA

^a Rasburicase is contraindicated in patients with glucose-6 phosphate dehydrogenase deficiency, known hypersensitivity to rasburicase, haemolytic anaemia or methemoglobinemia

^b Uric acid cutoff may be adjusted according to local guidance.

Recommended prophylaxis adapted from MD Anderson Cancer Center guidance ([Coiffier et al 2008](#)) and Cairo and Bishop ([Cairo and Bishop 2004](#)).

IV = intravenous; LDH = lactate dehydrogenase; TLS = tumour lysis syndrome; WBC = white blood cell.

F 1.2 AZD0466 Dose Modifications for Tumour Lysis Syndrome

AZD0466 dose modifications for TLS are summarised in [Table F29](#).

Table F29 AZD0466 Dose Modifications for Tumour Lysis Syndrome

Abnormality	Action with AZD0466
Laboratory findings (serum)	
Uric acid ≥ 475.8 µmol/L	
 Initiate supportive therapy as per standard clinical practice, additional guidance provided in Table F30.
Potassium ≥ 6.0 mmol/L	
Phosphate ≥ 1.6 mmol/L (5.0 mg/dL) with ≥ 0.16 mmol/L (0.5 mg/dL) increase ^a	
 Delay AZD0466 for up to 7 days (if finding present before administration of AZD0466) If resolution to within specified threshold in ≤ 7 days, restart at the same dose level If resolution after 7 days restart AZD0466 at one lower dose
Corrected calcium < 1.75 mmol/L	
Creatinine increase by > 26.5 µmol/L from baseline (creatinine > 1.5 × ULN if no baseline)	
All laboratory abnormalities must resolve to within specified threshold before AZD0466 is restarted	
Clinical findings	
Signs suggestive of clinical TLS (eg, acute kidney injury, cardiac arrhythmia/dysrhythmia ^b , hypotension ^c , heart failure ^c)	
 Initiate supportive therapy as per standard clinical practice Delay AZD0466 for up to 14 days AZD0466 at one lower dose following resolution

Table F29 AZD0466 Dose Modifications for Tumour Lysis Syndrome

Abnormality	Action with AZD0466

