Severe (≥ 7.0 mmol/L) or symptomatic	
 As above, plus Calcium gluconate^a 100 to 200 mg/kg by slow IV infusion if concurrent ECG changes (including life-threatening arrhythmias) Regular IV insulin and dextrose, monitor blood glucose closely Consider sodium bicarbonate ^a if patient is acidaemic Consider albuterol (to be avoided in patients with acute coronary disease) Dialysis may be required
Renal dysfunction (uraemia)	
 Fluid and electrolyte management Uric acid and phosphate management Adjust doses of renally excreted medication Dialysis or haemofiltration may be required

^a Sodium bicarbonate and calcium gluconate should not be administered through the same line.

Recommended management adapted from MD Anderson Cancer Center guidance and [Coiffier et al 2008](#).

ECG, electrocardiogram; IV, intravenous.

Laboratory parameters indicating TLS (including blood urea nitrogen, creatinine, phosphate/phosphorus, uric acid, calcium, potassium, and LDH) will be evaluated. Fluid balance must be monitored per institutional standards. If more aggressive hydration management is indicated, patient hospitalisation will be considered at Investigator discretion. Allopurinol prophylaxis should be considered based on institutional guidelines.

F 1.4 Reporting Adverse Events of TLS

The Investigator will report TLS as an adverse event or serious adverse event of “laboratory TLS” or “clinical TLS” according to the classification of TLS in Appendix [G 1](#). For the purposes of adverse event reporting, a CTCAE grade for TLS should also be recorded, as follows:

- CTCAE Grade 3: TLS present
- CTCAE Grade 4: TLS with life-threatening consequences; urgent intervention indicated
- CTCAE Grade 5: Death

Tumour lysis syndrome will also be graded according to Cairo-Bishop criteria for the purposes of dose-limiting toxicity assessment and summary of adverse events of special interest (Appendix [G 2](#); [Cairo and Bishop 2004](#)).

F 2 Guidance for Management of Haematologic Changes

F 2.1 Thrombocytopenia and Haemorrhage

Platelet transfusions are permitted as per institutional standards. However, due to the mechanism of action of AZD0466, platelet transfusion may have limited efficacy within 24 to 48 hours after AZD0466 infusion.

AZD0466 should be withheld in presence of significant bleeding events with or without thrombocytopenia, such as:

- Grade 3 or 4 haemorrhage
- Any grade serious haemorrhage event

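### Three laboratory limits are printed in two units that do not convert: TLS phosphate (Table G31), eligibility haemoglobin (Table 3) and, less importantly, rasburicase creatinine (Table F28)

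*Protocol*

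**What the plan says.** Three cells of the protocol each state one limit in two units.

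- **Phosphate**, Appendix G 1, Table G31, a criterion for laboratory TLS: "Phosphate $\geq 1.5 \text{ mmol/L}$ ($\geq 1.5 \text{ mg/dL").
- **Haemoglobin**, Section 5.1, Table 3, a core eligibility limit: at least 8.0 "g/dL (5.59 mmol/L").
- **Creatinine**, Appendix F 1.1, Table F28, one of three risk factors for using rasburicase: "Serum creatinine > 1.3 mg/dL (> 88.4" µmol/L).

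For comparison, Table F29 in Appendix F 1.2 gives a phosphate action level of "1.6 mmol/L (5.0 mg/dL").

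Section 8.2.4 says that safety laboratory work "will be performed at a local laboratory at or near to the Investigator site". Section 5 says that prospective approval of entry-criteria deviations, "also known as protocol waivers or exemptions, is not permitted". Appendix F 1.4 has the investigator report TLS by the Appendix G 1 classification and also record a CTCAE grade, the lowest being "CTCAE Grade 3: TLS present". Appendix G 2 adds that "The grade of the maximal clinical manifestation defines the overall grade of TLS". Neither document reconciles the three pairs or says which unit takes precedence.

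**The concern.** A limit given in two units should be one limit. If it is not, a patient's classification depends on the unit the local laboratory happens to use.

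**Haemoglobin.** The same patient can be eligible at one site and ineligible at another. Waivers are barred, and SAP Section 4.3.7 lists departure from entry criteria as its first deviation category.

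**Phosphate.** Laboratory TLS needs two metabolic abnormalities in the same 24 hours. If the mg/dL figure is applied literally, the phosphate criterion is met at about a third of the mmol/L limit, so one further abnormality could be enough. TLS is an adverse event of special interest (Protocol 8.3.6). A false call would be recorded as at least Grade 3 and would enter the TLS key-patient output (SAP 5.6.8.2). If judged related, it would also enter the table of related Grade 3 or higher events (SAP 5.6.2.2).

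**Creatinine.** Only a prophylaxis recommendation is touched; eligibility and TLS classification are not.

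**Working it through.** **Inputs.** The printed pairs come from Tables G31, F29, 3 and F28. The documents give no molar masses, so I take the standard constants: phosphorus 30.974, uric acid 168.11, calcium 40.078, creatinine 113.12 and haemoglobin monomer 16,114.5.

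**Formula.** mmol/L = (mg/dL × 10) / molar mass. For haemoglobin, mmol/L = (g/dL × 10 × 1000) / molar mass.

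**Controls: pairs in the same TLS tables that should convert.**

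- Uric acid (G31): 8.0 × 10 / 168.11 = 0.4759 mmol/L = 475.9 µmol/L. Printed 475.8; agrees.
- Corrected calcium (G31): 7.0 × 10 / 40.078 = 1.747 mmol/L. Printed 1.75; agrees.
- Phosphate (F29): 5.0 × 10 / 30.974 = 1.614 mmol/L and 0.5 × 10 / 30.974 = 0.161 mmol/L. Printed 1.6 and 0.16; both agree.

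So the protocol does use paired units to mean a single limit, and the method reproduces its correct pairs.

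**Phosphate, Table G31.**

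- 1.5 mmol/L = 1.5 × 30.974 / 10 = 4.65 mg/dL.
- 1.5 mg/dL = 1.5 × 10 / 30.974 = 0.484 mmol/L.
- Ratio: 0.484 / 1.5 = 0.32.

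The protocol's own factor gives the same answer without outside constants. From F29, 5.0 / 1.6 = 3.125 and 0.5 / 0.16 = 3.125 mg/dL per mmol/L. Hence 1.5 mmol/L = 1.5 × 3.125 = 4.69 mg/dL, and 1.5 mg/dL = 1.5 / 3.125 = 0.48 mmol/L.

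Expressing phosphate as PO4 mass (94.97) does not help: 1.5 mmol/L would be 1.5 × 94.97 / 10 = 14.2 mg/dL.

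**Haemoglobin, Table 3.**

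- 8.0 g/dL = 8.0 × 10 × 1000 / 16,114.5 = 4.96 mmol/L.
- 5.59 mmol/L = 5.59 × 16,114.5 / 10,000 = 9.01 g/dL.

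On a tetramer basis 8.0 g/dL would be 4.96 / 4 = 1.24 mmol/L, which is further away.

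**Creatinine, Table F28.**

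- 1.3 mg/dL = 1.3 × 10 / 113.12 = 0.1149 mmol/L = 114.9 µmol/L.
- 88.4 µmol/L = 0.0884 × 113.12 / 10 = 1.0 mg/dL.

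**Values on which the two printed figures disagree.**

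| Cell | Disagreement zone | Stricter or looser |
|---|---|---|
| Phosphate (G31) | 1.5 to below 4.65 mg/dL | mg/dL figure calls more TLS |
| Haemoglobin (Table 3) | 8.0 to below 9.0 g/dL (4.96 to below 5.59 mmol/L) | mmol/L figure excludes more patients |
| Creatinine (F28) | above 88.4 and up to 114.9 µmol/L | µmol/L figure counts more risk factors |

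**How far a false phosphate call travels.** Protocol 10.6.6.3 requires Cairo-Bishop Grade 3 or higher for a TLS dose-limiting toxicity. Table G32 assigns that grade on creatinine, arrhythmia or seizure. Phosphate alone therefore cannot produce a DLT; its reach is adverse-event and special-interest reporting.

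**The case against.** The strongest reply is that a digit was misread when the PDF was converted. If the phosphate cell really reads 4.5 mg/dL, it equals 1.45 mmol/L and the pair is sound. If the haemoglobin cell really reads 9.0 g/dL, it equals 5.59 mmol/L. This doubt is fair for either cell, and it is why the source pages should be checked first. It does not cover the creatinine cell as naturally, since 88.4 µmol/L is the exact conversion of 1.0 mg/dL rather than of 1.3. Dismissing the whole point would take three separate misreadings while neighbouring pairs came through intact.

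The second reply is that the harm is limited, and much of this stands. A phosphate of 1.5 mg/dL sits oddly under a hyperphosphataemia label, and Tables F29 and F30 use far higher values, so a careful investigator may see the slip. A second abnormality is still needed. Delays of AZD0466 for laboratory findings follow Table F29's own phosphate limit. Laboratory values and units are recorded, so a false call could be found later. For haemoglobin, if 8.0 g/dL is the intended limit, the error costs enrolment rather than exposing patients to risk. The Part B primary endpoint, objective response rate, is not touched.

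These replies bound the consequences but do not make the pairs agree. An eligibility limit and a TLS criterion should not depend on the reader spotting an error.

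**Conclusion.** The concern holds. As printed, all three pairs state different limits, by far more than rounding: about threefold for phosphate, 1 g/dL for haemoglobin, and 1.3 against 1.0 mg/dL for creatinine.

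Haemoglobin and phosphate should be fixed because the trial acts on them, the first for eligibility without waivers and the second for TLS reporting. Creatinine is minor. No effect on DLTs from phosphate alone, and so none on dose escalation by that route, is shown.

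The conclusion rests on the supplied text being a true reading of these cells and on standard molar masses; for phosphate, the protocol's own Table F29 factor suffices. The documents do not say which units sites report, so the number of patients affected cannot be estimated.

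**What to change.** 1. Check the three cells against the source pages. Drop any pair that proves to be a misreading.
2. Have the sponsor confirm each intended clinical limit, then correct the pair so both units agree. If the lead values are intended, they become:
   - phosphate at least 1.5 mmol/L (4.65 mg/dL)
   - haemoglobin at least 8.0 g/dL (4.96 mmol/L)
   - creatinine above 1.3 mg/dL (114.9 µmol/L)
3. Notify sites of the corrected limits.
4. For each error confirmed in the haemoglobin or phosphate cell, recheck the eligibility decisions or laboratory TLS calls already made in the affected units.

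The cost is up to three corrected table cells, one site notification and a limited data check. Neither the design nor the SAP changes.

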Appendix H Drugs That Prolong QT Interval and/or Induce Torsades De Pointes

Drugs with known or possible risk of Torsades de Pointes (cardiac arrhythmia due to drug-induced QTc prolongation) are withheld for 5 half-lives prior to the first dose of study intervention and will continue to be withheld during the study, and for 14 days after the last dose of AZD0466.

Table H33 Drugs with a Known Risk of Torsades de Pointes

Contraindicated drug	Withdrawal period prior to the start of study intervention
Aclarubicin, anagrelide, ciprofloxacin, clarithromycin, cocaine, droperidol, erythromycin, levofloxacin, ondansetron, papaverine hydrochloride, procainamide, sulpiride, sultopride, terfenadine, terlipressin.	2 days
Cilostazol, cisapride, disopyramide, dofetilide, domperidone, flecainide, gatifloxacin, grepafloxacin, ibutilide, moxifloxacin, oxaliplatin, propofol, quinidine, sotalol, roxithromycin, sevoflurane, sparfloxacin, thioridazine	7 days
Azithromycin, bepridil, chlorpromazine, halofantrine, haloperidol, mesoridazine, citalopram, dronedarone, escitalopram, fluconazole, levomepromazine, levosulpiride	14 days
Donepezil, terodilane	3 weeks
Levomethadyl, methadone, pimozide	3 weeks ^b
Arsenic trioxide ^a , ibogaine	3 weeks ^b
Pentamidine	3 weeks ^b
Astemizole, probucol, vandetanib	3 weeks ^b
Amiodarone, chloroquine	1 year

^a Estimated value, as pharmacokinetics of arsenic trioxide have not been studied.

^b The withdrawal period for these drugs will be 3 weeks prior to the start of study treatment, after discussion with the Study Physician regarding the risk/benefit ratio.

CredibleMeds® (www.crediblemeds.org) is the standard reference for drugs with known or possible risk of Torsades de Pointes. Since CredibleMeds® constantly assesses new drug information and updates its lists, sites should go directly to the crediblemeds.org website in real-time for reference. Patients receiving drugs listed in the “known” or “possible” categories at the time of eligibility assessment are prohibited from 14 days before the start of treatment until permanent discontinuation of treatment.

Some of the medications listed as a possible risk of Torsades de Pointes may be allowed at the Investigator’s discretion after approval by the Study Physician when the patient has unmet medical need to continue receiving prohibited medication(s), no suitable alternative treatments are available, and the benefit-risk ratio is acceptable in the Investigator’s opinion.

Appendix I Contraception Guidance

I 1 Definitions

- A female of childbearing potential is defined as a female who is not permanently surgically sterilised or postmenopausal.
- Surgical sterilisation includes hysterectomy and/or bilateral oophorectomy and/or bilateral salpingectomy but excludes bilateral tubal occlusion (the term occlusion refers to both occluding and ligating techniques that do not physically remove the oviducts).
- Postmenopausal is defined as amenorrhoeic for 12 months without an alternative medical cause. The following age-specific requirements apply:
 - Women under 50 years of age would be considered postmenopausal if they have been amenorrhoeic for 12 months or more following cessation of exogenous hormonal treatments AND with luteinising hormone and follicle-stimulating hormone levels in the postmenopausal range
 - Women over 50 years of age would be considered postmenopausal if they have been amenorrhoeic for 12 months or more following cessation of all exogenous hormonal treatments
- A highly effective method of contraception is defined as a method that results in a low failure rate (ie, less than 1% per year) when used consistently and correctly.

I 2 Contraception Methods

Highly effective methods of contraception are described in [Table I34](#).

Table I34 Highly Effective Methods of Contraception

Barrier/Intrauterine Methods	Hormonal Methods

• Intrauterine device• Intrauterine hormone-releasing system (UIS)^a• Bilateral tubal occlusion• Vasectomized partner^b• Sexual abstinence^c	
• Combined (oestrogen and progestogen containing hormonal contraception)
◦ Oral (combined pill)◦ Injectable◦ Transdermal (patch)• Progestogen-only hormonal contraception associated with inhibition of ovulation^d
◦ Injectable◦ Implantable

^a This is also considered a hormonal method.

^b With appropriate post-vasectomy documentation of surgical success (absence of sperm in ejaculate).

^c Sexual abstinence is considered a highly effective method only if defined as refraining from heterosexual intercourse during the entire period of the study and if it is the preferred and usual lifestyle of the patient. However, periodic, or occasional abstinence, the rhythm method, and the withdrawal method are not acceptable methods of contraception.

^d Progestogen-only hormonal contraception, where inhibition of ovulation is not the primary mode of action (eg, minipill), is not accepted as a highly effective method.

